4. OBJECTIVES, ENPOINTS/OUTCOMES AND OTHER STUDY VARIABLES

4.1 Objectives

(STROBE 3) [6]

Zürich Exhalomics is a flagship project of the Universities of Zürich (University of Zürich and ETHZ) and the department of paediatric pneumology of the University Children's Hospital Zürich is part of this interdisciplinary consortium. We plan a clinical study to investigate specific breath prints and molecules for the assessment and prediction of children with chronic respiratory symptoms by breath analyses with SESI-MS.

We plan to reach this aim by answering following research questions:

- Do breath prints separate healthy preschool children differ from their peers with respiratory symptoms? (WP I, see below)
- Do breath profiles differ among symptomatic preschool children? (WP I)
- Is there an association between breath profiles and conventional clinical phenotypes? (WP I)
- Is breath analysis by SESI-MS in preschool age diagnostic for PBB? (WP I)
- Do the breath profiles in preschool age predict outcomes later in life (asthma, transient wheeze)? (WP I & II)
- Do breath prints differ between healthy school-aged children differ and their asthmatic peers diagnosed by conventional methods (clinics, lung function, allergy testing)? (WP III)
- Can SESI-MS distinguish between controlled and uncontrolled asthma? (WP III)
- Can phenotyping by SESI-MS in school-age children be replicated in a second population? (WP II & III)
- Which single biomarkers for distinct respiratory diseases can be extracted from breath profiles from preschool and school-aged children? What is their role in disease pathogenesis? (WP I, II & III)
- How can SESI-MS analysis be streamlined for routine clinical use? (WP I, II & III)
- Are breathprints associated with microbial colonisation, symptoms, and clinical history? (WP I, II & III)

Our research hypotheses are:

- The development of asthma later in life can be predicted by specific breath prints and/or specific molecules in exhaled breath in preschool children with chronic respiratory symptoms
- The diagnosis of protracted bacterial bronchitis can be preponed by breath analysis in preschoolers with chronic cough
- Breath analysis is capable to classify school-aged children with and without asthma (breath prints and/or specific molecules in exhaled breath)
- Specific breath prints predictive for asthma in school age can also be found in preschool children that are likely to develop asthma later in life

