7.3 Planned analysis

(STROBE 12a-d) [6]

Demographic and clinical characteristics will be compared using independent-sample pairwise analysis methods (i.e. ANOVA, t-tests, Mann-Whitney U-tests) with Bonferroni-correction for multiple comparisons. Exhaled breath composition will be evaluated through a stepwise application of statistical data reduction approaches. Bonferroni-corrected, non-parametric one-way analyses of variance (Kruskal-Wallis tests) will be employed to select significant discriminatory mass-to-charge (*m/z*) peaks. Thereafter, principle component analysis, multivariate analysis of variance and canonical analysis will be used to extract meaningful summary statistics. Data analysis will be done with Matlab (R2016b and newer, The MathWorks Inc., Natick, MA, US) and R (Development Core Team, R Foundation for Statistical Computing, Vienna, Austria) based on data analysis tools developed at ETH Zurich. The SESI-MS data will be acquired and mass calibrated with the Analyst TF 1.7 and PeakView 2.1 software (Applied Biosystems Sciex, Toronto, ON, Canada).

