7.3.1 Datasets to be analysed

The final dataset will include patient characteristics, clinical data, and data from the questionnaires and the selected features from SESI-analysis.

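### Section 7.3 selects peaks on group labels and then runs MANOVA and canonical analysis on them with no independent or resampled evaluation, so the MANOVA p-value is uninformative and the separation shown is optimistic

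*Protocol*

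**What the plan says.** Protocol section 7.3 describes a fixed order of steps: "Exhaled breath composition will be evaluated through a stepwise application of statistical data reduction approaches". The first step uses the group labels: "Bonferroni-corrected, non-parametric one-way analyses of variance (Kruskal-Wallis tests) will be employed to select significant discriminatory mass-to-charge" peaks. The second follows from it: "Thereafter, principle component analysis, multivariate analysis of variance and canonical analysis will be used to extract meaningful summary statistics". Section 7.3.1 lists "the selected features from SESI-analysis" as the breath part of the final dataset.

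No data split, cross-validation, permutation or external test set is attached to these steps. The family over which Bonferroni is applied is not named, nor is the number of principal components to keep.

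Sections 7.1 and 7.2 call the work exploratory. The aims go further. Section 3.2 makes proof that SESI-MS can discriminate the main objective, together with its transfer to routine care. Section 4.1 hypothesises: "Breath analysis is capable to classify school-aged children with and without asthma". It also asks whether breath in preschool age is diagnostic for protracted bacterial bronchitis, and it asks about the two symptomatic groups: "Do breath profiles differ among symptomatic preschool children? (WP I"). Groups are 60/60/60 in WP I and 30/30/30 in WP III.

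**The concern.** A peak reaches the second stage only because it already differs between the groups in these children. Testing the same groups on that peak in the same children repeats the screen; it does not test it. Canonical axes are also chosen to maximise separation of the same labels, so a plot or classification made from them looks better than it would in the next child.

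The screen is an omnibus three-group test. A peak that separates healthy from ill passes it legitimately and then enters an analysis that also displays high against low asthma risk, a contrast for which it may carry no information.

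The hypotheses concern classification, prediction and diagnosis, which are statements about new children. Separation in the selection sample does not measure that.

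**Working it through.** The plan gives no figure to reproduce here, so the stated chain was simulated under assumptions.

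**Inputs.** Group sizes come from sections 5.1 and 7.1. The number of peaks is not stated: 3,500 is borrowed from section 3.1.4.3, where it counts identified breath components, and 1,000 was also tried. Familywise alpha 0.05 is assumed. Correlation, effect size and number of differing peaks are assumed. Linear discriminant classification stands for the canonical step. Apparent means scored in the selection sample; new means scored in a fresh sample.

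**Step 1: no peak differs in any group.** With Bonferroni over all m peaks the per-peak threshold is 0.05/m, that is 0.05/3,500 = 1.43 × 10⁻⁵. For independent peaks the chance that any passes is at most 1 − (1 − 0.05/3,500)^3,500 = 4.9%. Simulated, it was 1.7-3.4%. When a peak did pass, MANOVA was below 0.05 every time (median p about 10⁻⁶ to 3 × 10⁻⁵). Apparent accuracy was then 46% at 60 per group and 51-53% at 30, against 32-34% in new children (chance is 33%).

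**Step 2: the same null, but Bonferroni only over the three group pairs.** The threshold is 0.05/3 = 0.0167, so with 1,000 peaks about 1,000 × 0.0167 = 17 would pass by chance. Simulated means were 15.8 (60 per group) and 15.0 (30 per group). Every null dataset showed false separation: apparent accuracy 69% and 81%, against about 34% in new children.

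**Step 3: a real shift in one group, 20 of 1,000 peaks, Bonferroni over all peaks, no PCA.** Figures apply to datasets in which at least one peak passed.

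| Per group | Shift | Apparent | New | Gap |
|---|---|---|---|---|
| 60 | 0.5 SD | 50.3% | 41.8% | 8.5 |
| 30 | 0.5 SD | 50.7% | 38.3% | 12.4 |
| 60 | 0.7 SD | 66.6% | 55.1% | 11.5 |
| 30 | 0.7 SD | 54.4% | 43.8% | 10.6 |

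**Step 4: symptomatic differ from healthy, high and low risk identical.** 3,500 peaks in blocks of 10 with correlation 0.8, threshold 0.05/3,500, 0.8 SD shift, PCA to 90% of variance, 60 replicates per setting.

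| Per group | Shifted peaks | Three groups, apparent / new | Identical risk groups, apparent / new |
|---|---|---|---|
| 60 | 200 | 79% / 63% | 72% / 50% |
| 60 | 20 | 54% / 47% | 58% / 50% |
| 30 | 500 | 80% / 59% | 74% / 50% |

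The best attainable three-group accuracy here is 1/3 × 1 + 2/3 × 0.5 = 67%: healthy children always right, risk groups by coin toss. Anything above that is noise. Over all settings tried, including other choices of component number, three-group accuracy was 51-87% apparent against 46-66% new, and the identical groups 56-84% against about 50%.

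**Step 5: what drives the gap.** Keeping 3 components instead of enough for 90% of variance lowered the identical-group figure from 84% to 57%. In a check with 200 shifted peaks, 60 per group and block correlation 0.5, about 51 components gave 83% with selected peaks and 81% with the same number of randomly chosen null peaks. Most of the large gaps therefore come from fitting many components to few children and scoring the same children.

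**The case against.** Several points on the other side stand.

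- The screen is Bonferroni-corrected. A Kruskal-Wallis test is a single test across the groups, so the number of peaks is the natural family. On that reading nothing reaches stage two in at least about 95% of fully null datasets.
- The largest gaps come from retaining many components, and the plan fixes no such number. It calls the steps data reduction, which suggests few.
- Section 7.2 names patients against healthy controls as the comparison. At 60 per group that contrast was inflated by only about 1-5 points. At 30 per group one check gave 94-95% apparent against 84-86% in new children.
- Section 7.3 plans summary statistics and promises no accuracy, sensitivity or AUC. The study is labelled exploratory.
- Section 4.1 looks beyond one sample: it asks about replicating school-age phenotyping across WP II and III and about preschool profiles predicting later outcomes, and it hypothesises that school-age prints recur in preschoolers.
- Validation detail is often left to an analysis plan, which is not at hand. That selection and testing use the same children is inferred from the absence of any stated split. Section 7.3.4 allows methods to be updated.

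What does not stand: the exploratory label does not fit aims of discrimination and diagnosis. No analysis in section 7.3 is linked to the replication questions, and none of them tests high against low risk in WP I. The order of steps is written down, so the difficulty is the stated sequence and not only missing detail.

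**Conclusion.** The point holds in a limited form. Followed as written, section 7.3 gives a MANOVA p-value that carries no information beyond the screen, and a picture of separation that is optimistic. The contrast most exposed is high against low asthma risk, because Bonferroni does not protect it when healthy and ill children truly differ, and section 3.2 already regards such a difference as well supported.

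A reader might infer that the chain creates separation wherever none exists. The documents do not support that: with the family taken as all peaks, the error under a global null is about 5% at most. It would be true only under the narrower family in step 2, which the text leaves open. Nor do they support saying that the plan will report inflated accuracy, since no accuracy figure is planned, or that the healthy-versus-symptomatic result is worthless.

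The sizes (56-84% against about 50% for identical groups; about 5-23 points for three groups; about 1-5 for symptomatic versus healthy at 60 per group) rest on assumed peak number, correlation, effect and component count. The direction was the same in every setting tried. Severity: should-fix.

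**What to change.** Amend section 7.3 as follows.

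- State that the Bonferroni family is all m/z peaks.
- Label MANOVA and canonical results on selected peaks as descriptive.
- For any classification, prediction or diagnostic claim, repeat peak selection, scaling, PCA and canonical analysis inside each training fold of stratified cross-validation, and report only out-of-fold performance.
- Select peaks for the contrast in question (symptomatic v healthy, high v low risk, asthma v healthy, allergic v non-allergic), not from the omnibus test.
- Take the p-value from permuting group labels and rerunning the whole chain.
- Fix the WP III signature before it is applied to WP II.

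Section 7.3.1 should keep the full peak table, because selection cannot be repeated inside folds if only the selected features are retained.

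The cost is code and computing time, and reported separation that will look less favourable. No extra children or procedures are needed.

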7.3.1 Datasets to be analysed

The final dataset will include patient characteristics, clinical data, and data from the questionnaires and the selected features from SESI-analysis.

7.3.2 Handling of missing data

As the study is depending on successful SESI-measurements, we will recruit further patients and controls to replace / compensate missing data and drop-outs for primary outcomes. Missing data from secondary outcomes will be acknowledged accordingly in the statistical analyses.

7.3.3 Ancillary analysis

Ancillary analyses will be planned based on the results from the primary statistics.

7.3.4 Deviations from the original statistical plan

The mathematical and statistical development in the analysis of large, multidimensional datasets is highly dynamic and improvement of the available methods are likely to occur in the near future. As we

closely collaborate with the ETH department of Computer Science, our data will be analysed state-ofart and any deviation from the planned analyses will be reported in the respective scientific articles.

8. DATA AND QUALITY MANAGEMENT

(HRO Art. 5, 25-27, Annex 2/1.7) [4]

8.1 Data handling and record keeping / archiving

(HRO Art. 5, 26, 27, Annex 2/1.7)

Paper documents and informed consent forms will be stored in a lock-secured cupboard in a dedicated research office (SP.C06) at the Division of Respiratory Medicine, University Children's Hospital of Zurich. Only study investigators have access to these documents. Authorised staff of the responsible ethics committee can request access to these data for monitoring and auditing purposes.

Electronic data will be stored in a password-secured coded spreadsheet file. The file will be stored within the Division of Pulmonology section of the University Children's Hospital of Zurich intranet server. It can only be accessed by authorised users from registered computers at the University Children's Hospital of Zurich.

8.2 Confidentiality, Data Protection

(HRO Art. 5) [4]

Data generation, transmission, storage and analysis of health related personal data and the storage of biological samples within this project will follow strictly the current Swiss legal requirements for data protection and will be performed according to the Ordinance HRO Art. 5.

Health related personal data captured during this project and biological samples from participants are strictly confidential and disclosure to third parties is prohibited; coding will safeguard participants' confidentiality.

Data protection: project data shall be handled with uttermost discretion and only be accessible to authorised personnel. Include a statement that direct access to source documents will be permitted for purposes of monitoring, audits or inspections and should declare who will have access to project plan, dataset, statistical code, etc. during and after the research project (publication, dissemination).

Strict participant confidentiality in accordance with established best clinical practice and Swiss legal requirements will be adhered to88. Only medically trained investigators will have access to clinical records. Once consented, all participant data used for analysis will be stored in a coded and secure format. Each participant will receive a code of the study location (e. g. continuous number according to time of enrolment continued by letters identifying the health status (CF or healthy control) and finished by a planned date of investigation). Patient details will be anonymous to anybody except authorised study investigators. A password secured electronic file only accessible by the principle investigator and his designee will act as the only link between the participants will not be identifiable from the results as submitted for publication. Data analysis will only use coded data records. Patients agree to confidential, coded use of information contained in their clinical records for research purposes as outlined in this protocol. Participants are informed that authorised staff of the responsible ethics committee of the Canton of Zurich, Switzerland, can obtain access to confidential information for monitoring and auditing purposes under strict adherence to confidentiality rules.

8.3 Coding

(HRO Art. 25-27) [4]

Each participant will receive a code of the study location (e. g. continuous number according to time of enrolment continued by letters identifying the health status (child with chronic respiratory symptoms or healthy control) and finished by a planned date of investigation). Patient details will be anonymous to anybody except authorised study investigators.

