5.4 Methods of minimising bias

(STROBE 9; swissethics 2) [6,69]

Selection bias: to reduce selection bias all patients with respiratory symptoms fulfilling the inclusion criteria for one of the work packages are asked to participate in the study. Healthy children will be recruited for the general population.

Loss for follow up may occur in the WP II and WP IV. As these children are followed up in the regular outpatient clinic in the same structure loss for follow up we expect to be not higher than 25 %.

Observer bias: the parents will fill in health questionnaires. Investigators performing the measurements are blinded to the clinical data and questionnaire results.

Sequential testing bias: All of the planned measurements will be performed in random order.

Measurement bias: feasibility study has been performed to reduce the measurement bias, tidal breathing with face mask vs single breath with mouthpiece were tested showing comparable results. The mask with the lowest level of plasticizers has been selected [79].

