6.8 Assessment of safety and reporting

(HRO Art. 20. 21) [4]

This project is categorized as a non-clinical research project, risk category B.

Participants will not be subjected to any invasive or distressing test or intervention procedures beyond routine clinical management plan. Other than sparing about one hour of their time to travel to and from the Kinderspital, blowing through a sterile mouthpiece and mask, participants will not experience any additional inconveniences. All investigators and participants are fully informed about the study design and no concealment or group allocation is necessary. All measurements will be undertaken by a small set of trained investigators in a standardised fashion. Participant confidentiality is a priority.

No adverse events are expected to arise from this study.

All measurements will be supervised by medically trained investigators. All participant contact will take place in the Kinderspital, guaranteeing easy and quick access to emergency alert systems and resuscitation equipment.

The primary outcome – breath analysis – involves a single, 20 min session that asks comfortably-seated participants to exhale calmly into a plastic mouth piece and mask connected to the mass spectrometer. Participants exhale six times interspersed with adequate rest periods without excessive force into the SESI-MS. They are not exposed to any environmental hazards like radiation or chemical vapours.

Thus, breath sampling is a non-invasive, harmless, effortless procedure that is not expected to entail any distress other than the minor inconvenience of traveling to the Kinderspital Zurich.

Only procedures with minimal risk and burden (questionnaire, breath collection, lung function, throat and nasal swaps, sputum collection and skin prick testing) are applied. Healthy controls may experience some itching after skin prick test (usually up to 15 minutes) in case of having sensitization to an allergen. As a routine procedure, local antihistamine gel will be applied on that area of skin to relief and decrease the duration of itching.

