7.2 Data processing

Paper documents and informed consent forms will be stored in a lock-secured cupboard in a dedicated research office at the Division of Pulmonology, University Children's Hospital of Zurich. Only study investigators have access to these documents. Authorised staff of the responsible ethics committee can request access to these data for monitoring and auditing purposes.

Electronic data will be stored in a password-secured coded spreadsheet file. The file will be stored within the Division of Pulmonology section of the University Children's Hospital of Zurich intranet server. It can only be accessed by authorised users from registered computers at the University Hospital of Zurich.

In the current study, exploratory comparisons between patients with chronic respiratory symptoms and healthy controls' breathprints shall be undertaken through statistical data reduction techniques. As previously demonstrated, this approach can drastically limit the number of compounds-of-interest – a crucial necessity for translating breathprint analysis into day-to-day clinical care [76].

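### The participant code shows case or control status, which undermines the observer-bias safeguard of section 5.4 for the patient-versus-control comparison if recordings are handled under that code

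*Protocol*

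**What the plan says.** Section 5.4 offers one safeguard against observer bias on the measurement side: "Investigators performing the measurements are blinded to the clinical data and questionnaire results". It does not name case/control group, and it says nothing about those who process or analyse the data.

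Section 8.3 sets out the coding: "Each participant will receive a code of the study location". The format, introduced as an example, is a running number in order of enrolment, then "letters identifying the health status (child with chronic respiratory symptoms or healthy control", and it is "finished by a planned date of investigation". Section 8.2 gives the same scheme with another case label, "letters identifying the health status (CF or healthy control", and adds: "Data analysis will only use coded data records". Section 8.2 also provides a password-protected link file open only to the principal investigator and a designee.

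Section 7.2 names the comparison of interest as "exploratory comparisons between patients with chronic respiratory symptoms and healthy controls". Sections 5.3 and 6.8 both state: "All investigators and participants are fully informed about the study design and no concealment or group allocation is necessary".

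**The concern.** Section 5.4 means the people taking the measurements to work without knowing the child's clinical picture. The code states the most decisive part of that picture. A child is a patient because of a history of wheeze or cough or an asthma diagnosis (section 6.1), and a control's respiratory health is established by questionnaire (sections 5.3 and 6.6). A letter for symptomatic or healthy therefore summarises what section 5.4 says is withheld.

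The primary outcome is the breath composition itself (section 4.2.1). Two provisions allow judgement to affect it before any test is run:

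- Section 7.3.2 makes the study depend on successful breath measurements and replaces participants whose primary data are missing. Whatever counts as successful decides who is in the dataset.
- Section 7.3.1 carries only selected breath features into the final dataset.

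If group is visible when a recording is accepted or its peaks are extracted, patients and controls may be handled differently. The resulting difference would look like the discriminating signal the study seeks.

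**Working it through.** The protocol gives no figure to reproduce on this point. The check compares the statements with one another and then counts the comparisons affected.

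1. **What is withheld, and from whom.** Under 5.4, clinical data and questionnaire results are withheld from the measuring investigators. Group is covered only by implication.

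2. **What the code discloses.** Under 8.2 and 8.3 it has two status levels, case and control. It carries no risk score, allergy result, lung function value or questionnaire answer.

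3. **When the code can exist.** It ends with the planned date of investigation, so it can be formed before the measurement visit.

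4. **Who works under it.** Section 8.2 ties analysis to coded records, so on the format described analysts see the status letters. No section says that acquisition files carry the code or that the operator sees it. That step is likely, but it is an inference.

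5. **How many children.** WP I has 60 + 60 + 60 = 180 and WP III has 30 + 30 + 30 = 90, together 270. Controls number 60 + 30 = 90 and cases 120 + 60 = 180. Every one of them receives a code.

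6. **Which contrasts the letters expose.** Each of the two work packages has three groups and so three pairwise comparisons.
   - WP I: control versus low risk and control versus high risk are exposed. Low versus high risk (60 versus 60) is not.
   - WP III: control versus allergic asthma and control versus non-allergic asthma are exposed. Allergic versus non-allergic asthma (30 versus 30) is not, as the code is worded.
   - Total: 2 + 2 = 4 of 6 exposed.

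7. **Other routes to the same information.** In WP I, section 5.2 limits exhaled nitric oxide to healthy controls, and section 5.4 has the measurements done in random order. An operator may therefore learn the group from the procedures, sometimes before the breath recording. Changing the code does not close this route.

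8. **Where group is needed.** Section 7.3 selects peaks with Bonferroni-corrected Kruskal-Wallis tests, which require group labels. Masking can extend up to that step and no further.

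9. **Whether the code text is sound otherwise.** Section 8.2 labels cases as cystic fibrosis, which section 6.2 excludes. Under section 6.3 a control who develops chronic symptoms leaves the control group, so the letter in that child's ID would become wrong. The text needs correction in any event.

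**The case against.** A reader might infer that the code abolishes the blinding on every record, and that sections 5.4, 6.8 and 8.3 cannot all be true. The documents do not support this, for four reasons.

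- Section 5.4 does not promise blinding to group. A two-level letter leaves the detailed clinical data, risk scores and allergy results hidden. Several questions in section 4.1 concern differences among symptomatic children, and the code does not touch those.
- The sentence on concealment in 5.3 and 6.8 can simply mean that an observational study has no allocation to conceal. It is unclear beside 5.4, but it is not a clear denial of masking.
- The code format is an example, and its use on raw breath files is not stated.
- Operator discretion is less than one might suppose. The number of repeats is fixed at six for mouthpiece measurements and for sleeping infants, and section 6.8 gives six in general. Only the description for ages 1.5 to 4 years omits a count. Rules for accepting recordings or choosing peaks are not described and may belong in a statistical analysis plan that is not shown.

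It can also be said that a neutral ID alone would not mask operators, given the nitric oxide measurement in WP I controls and the small team that measures.

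All of this limits the claim. What remains is that the protocol prescribes status letters in the only code it describes, requires analysis under coded records, and relies on blinding as its observer-bias safeguard. Leaving details to an analysis plan does not remove the letters from the protocol.

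**Conclusion.** The point holds in a limited form. The code in 8.2 and 8.3 discloses case/control status and so undermines the safeguard of 5.4 for comparisons with healthy controls, four of the six pairwise group comparisons in WP I and WP III. Comparisons among symptomatic or asthmatic children are unaffected by it.

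This rests on two assumptions: that the example format is the one used, and that recordings are labelled or preprocessed under it. The first is the plain reading, since no other format appears. The second is likely but unstated for acquisition. The protocol offers nothing from which to estimate a direction or size of bias, so the finding is a weakened safeguard and not a demonstrated distortion. It should be corrected because the remedy is cheap and protects the primary outcome.

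**What to change.** 1. In 8.2 and 8.3, replace the format with a sequential ID that carries no status letters. Hold group in the restricted link file already described in 8.2. This also removes the cystic fibrosis label and the difficulty of a control who later changes group.
2. State that acceptance of recordings, peak picking and alignment are done under the neutral ID. Release group only when the peak table is locked, and before the Kruskal-Wallis selection, which needs it.
3. In 5.4, state that masking covers case/control group as far as feasible.
4. In 5.3 and 6.8, clarify that the sentence on concealment refers to allocation.

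The cost is a new ID format, a few sentences and the management of a key file. No assessment, visit or sample size changes. Operators may still infer group from other procedures, such as nitric oxide in WP I controls only, so the benefit at the measurement visit is partial and that at preprocessing is the more certain.
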